### **7.14 Appropriateness of Measurements**

The measures of efficacy selected in the study differ for each of the 3 groups of infection, but in general includes both clinical and microbiologic outcome. The specific endpoints based on the EMA guidance [17] have been discussed with regulatory agencies.

The safety evaluations selected for the study are typical of those for this patient population and type of investigation, and utilize widely accepted measures.

### **7.15 Acceptable Time Windows**

Measurements for efficacy or safety endpoints will be performed according to the schedule of assessments as shown in Appendix 1. The following time window, as shown in Table 7-2, is acceptable.

**Table 7-2 Acceptable Time Windows**

	Study Activity	Acceptable Time Window
Screening	---	-48 hours
Randomization	Day 1	---
Day 3 Blood PK Sampling	Day 3	+ 2 days
Day 3 Blood PK Sampling (This sample should be drawn after the patient had at least 6 infusions)	Just prior to the next infusion	-1 to 0 hours
	One (1) hour into the infusion	± 15 minutes
	At the end of infusion	-15 minutes to end of infusion
	One (1) hour after end of infusion (four [4] hours after the start of infusion)	± 0.5 hours
EA	Day 3 to 4	+ 1 day
EOT	Last day of study treatment	As soon as possible after last dose (within 24 hours after the last dose)
TOC	EOT + 7	± 2 days
FUP	EOT +14	± 3 days
EOS	EOT +28	± 3 days

## 8. STUDY ACTIVITIES

The overall schedule of events for the study is presented in Appendix 1.

### 8.1 Screening (Day –2 to Randomization)

- Informed consent
- Appropriate clinical specimens will be obtained from all patients within 48 hours prior to the start of the infusion of the first dose of study treatment including blood for culture. Clinical specimens obtained by the site within the 48 hours prior to signing ICF could be acceptable as screening/baseline cultures for this study.
- Rapid diagnostics for the presence of a carbapenemase (if necessary)  
If any diagnostics provided by the sponsor are considered investigational in the country where the protocol is implemented are to be used, or diagnostics that are not the local standard of care for determination of carbapenem resistance are to be used, the investigational diagnostics section of the informed consent form will be required. (See Section 7.1)
- Inclusion and exclusion criteria assessments
- Baseline patient characteristics
- Medical history
- Physical examination including height and body weight
- Vital signs (including blood pressure, body temperature, pulse rate, and respiratory rate)
- 12-lead ECG
- Pregnancy test if applicable
- Clinical laboratory tests (hematology, blood chemistry, urinalysis, specialized tests and others; see Table 7-1)
- Glasgow Coma Scale
- Calculate APACHE II score
- Calculate SOFA score
- Provide parameters for CPIS score (HAP/VAP/HCAP patients)
- Clinical assessment of signs and/or symptoms
- Oxygenation status (patients receiving an oxygen inhalation treatment)
- Chest radiographs (HAP/VAP/HCAP patients)
- Biologic tissue or fluids (including blood) for microbiological culture
- AE assessment (begins with the signing of the informed consent form and continues through to the EOS)
- Prior and concomitant therapies
- Hospitalization

## **8.2 Treatment Period (Day 1 to up through Day 14)**

### **8.2.1 Randomization and Treatment Initiation Day 1**

- Randomize patient via IWRS or IVRS
- Initiate treatment based on eGFR and CrCl by Cockcroft-Gault equation

### **8.2.2 All Treatment Days**

- Continue randomized treatment
- Vital signs including body temperature
- Concomitant therapy
- AE assessment
- Hospitalization
- Vital status (survival)
- Dose adjustment considered on review of renal function conducted per local clinical practice (If necessary)

### **8.2.3 Treatment Day 3**

- Activities for all treatment days (See Section 8.2.2)
- Blood PK samples (after at least 6 infusions) for patients receiving S-649266
- Ventilator parameters at the timing of blood PK sampling for ventilated patients (See Section 7.8.1.4)

### **8.2.4 Early Assessment (EA) (Occurs once at investigator's discretion during Days 3 to 4)**

- Activities for all treatment days (See Section 8.2.2)
- Limited physical examination relevant to the patient's current condition
- Clinical laboratory tests (hematology, blood chemistry, urinalysis, and others; see Table 7-1)
- Glasgow Coma Scale
- Calculate SOFA score
- Provide parameters for CPIS score (HAP/VAP/HCAP patients)
- Clinical assessment of signs and/or symptoms
- Oxygenation status (patients receiving an oxygen inhalation treatment)
- Chest radiographs (HAP/VAP/HCAP patients)
- Biologic tissue or fluids (including blood until result is negative) for microbiological culture
- Assess clinical outcome
- Assess microbiological outcome
- Dosing adjustment if renal function is changed
- Blood PK samples for patients with nonstable renal function resulting in a dosing

- adjustment at EA (S-649266 group only) (See Section 7.9.1)
- Ventilator parameters at the timing of blood PK sampling for ventilated patients (See Section 7.8.1.4)

### **8.2.5 Treatment Day 14**

In case treatment duration is extended beyond 14 days, an additional assessment will be conducted on Day 14.

- Activities for all treatment days (See Section 8.2.2)
- Limited physical examination relevant to the patient's current condition
- Clinical laboratory tests (hematology, blood chemistry, and urinalysis; see Table 7-1)
- Glasgow Coma Scale
- Calculate SOFA score
- Provide parameters for CPIS score (HAP/VAP/HCAP patients)
- Clinical assessment of signs and/or symptoms
- Oxygenation status (patients receiving an oxygen inhalation treatment)
- Chest radiographs (HAP/VAP/HCAP patients)
- Biologic tissue or fluids (including blood until result is negative) for microbiological culture
- Assess clinical outcome
- Assess microbiological outcome

### **8.2.6 Last Day of Study Treatment (EOT)**

- Activities for all treatment days (See Section 8.2.2)
- Limited physical examination relevant to the patient's current condition
- Clinical laboratory tests (hematology, blood chemistry, and urinalysis; see Table 7-1)
- Glasgow Coma Scale
- Calculate SOFA score
- Provide parameters for CPIS score (HAP/VAP/HCAP patients)
- Clinical assessment of signs and/or symptoms
- Oxygenation status (patients receiving an oxygen inhalation treatment)
- Chest radiographs (HAP/VAP/HCAP patients)
- Biologic tissue or fluids (including blood until result is negative) for microbiological culture
- Assess clinical outcome
- Assess microbiological outcome

### **8.3 Test of Cure (TOC [EOT + 7 days])**

- Limited physical examination relevant to the patient's current condition
- Vital signs (including blood pressure, body temperature, pulse rate, and respiratory rate)
- Clinical laboratory tests (hematology, blood chemistry, urinalysis, and specialized tests; see Table 7-1)
- Clinical assessment of signs and/or symptoms
- Oxygenation status (patients receiving an oxygen inhalation treatment)
- Chest radiographs (HAP/VAP/HCAP patients) (if indicated)
- Biologic tissue or fluids (including blood until result is negative) for microbiological culture
- Glasgow Coma Scale
- Calculate SOFA score
- Provide parameters for CPIS score (HAP/VAP/HCAP patients)
- AE assessment
- Concomitant therapy
- Assess clinical outcome
- Assess microbiological outcome
- Hospitalization

### **8.4 Follow-up (FUP [EOT + 14 days])**

- Limited physical examination relevant to the patient's current condition
- Vital signs (including blood pressure, body temperature, pulse rate, and respiratory rate)
- Clinical laboratory tests (hematology, blood chemistry, and urinalysis; see Table 7-1)
- Clinical assessment of signs and/or symptoms
- Oxygenation status (patients receiving an oxygen inhalation treatment)
- Chest radiographs (HAP/VAP/HCAP patients) (if indicated)
- Biologic tissue or fluids (including blood until result is negative) for microbiological culture (if indicated)
- Glasgow Coma Scale
- Calculate SOFA score
- Provide parameters for CPIS score (HAP/VAP/HCAP patients)
- AE assessment
- Concomitant therapy
- Assess clinical outcome
- Assess microbiological outcome
- Hospitalization

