## **7.7 Clinical Laboratory Tests**

### **7.7.1 Microbiologic Cultures**

Appropriate clinical specimens will be obtained from all patients within 48 hours prior to the start of the infusion of the first dose of study treatment or clinical specimens obtained by the site within the 48 hours prior to signing ICF could be acceptable as screening/baseline cultures for this study.

For patients who failed empiric treatment (as defined in general inclusion No. 4), clinical specimens obtained within 72 hours of randomization in this study could be used as screening/baseline cultures. A culture should be done again upon randomization and the pathogen isolated sent to central lab.

Biologic tissue or fluids for microbiologic cultures will be sent to the local laboratory for identification of all pathogens causing the infection. After initiation of study treatment, appropriate clinical specimens will be obtained at the specified assessment time points (EA, EOT, TOC, FUP. If it is not possible to obtain an appropriate clinical specimen after randomization, the reason (eg, no material available to culture) must be documented in the eCRF.

In addition, 2 blood samples from separate venipunctures will be obtained from all patients regardless of the site of infection, within 48 hours prior to the start of study treatment and sent to the local laboratory. Subsequent blood cultures are to be repeated only if the baseline blood culture is positive.

Culture results should be recorded in the eCRF with the date of sampling and the reporting date and identified isolates sent to the central lab.

In general, all specimens should also have Gram stain of infected material (not swab). A report of both inflammatory cells and bacteria is necessary.

Inappropriate clinical specimens should not be used for confirmatory culture identification of causative pathogens.

Detailed procedures (Gram stain, quantitative or semi-quantitative cultures) per infection type are provided in Appendix 4.

All isolated pathogens (Gram-positives, Gram-negatives, fungi and yeast) will be frozen and stored for later shipping to the central laboratory. Detailed procedures for sample

collection, handling, labeling, storage, and shipping will be provided in the separate study procedure manual. Shipping labels, instructions for shipping, and courier service will be provided from the sponsor or CRO.

[figure not shown]

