#### 7.11.4.2 cUTI

- **Sustained Eradication:** A culture taken any time after documented eradication at TOC, and a urine culture obtained at FUP shows that the baseline uropathogen found at entry at  $\geq 10^5$  CFU/mL remains  $< 10^3$  CFU/mL.
- **Recurrence:** A culture taken any time after documented eradication at TOC, up to and including FUP that grows the baseline uropathogen  $\geq 10^3$  CFU/mL
- **Indeterminate:** No urine culture or patient received additional antibacterial therapy for the treatment of the current infection including missed sampling.

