#### **6.4.2 Missing Microbiological or Clinical Outcome**

For clinical and microbiological outcomes, subjects who are lost to follow-up or have missing or "indeterminate" outcomes will be included in the denominator as indeterminate for cure/eradication rate, i.e., considered as not responders. If judged by the investigator that a subject died due to pneumonia, BSI/sepsis or cUTI, the clinical outcome will be considered as clinical failure after the event of death. If a subject died due to other reasons, the clinical outcome will be considered as "indeterminate" after death.

For clinical outcome, if a subject received additional antibiotics for target disease (i.e., baseline infection) before the target date, the outcome will be considered as "clinical failure". If a subject did not receive additional antibiotics for target disease before the target date, the outcome will be considered as "indeterminate".

Missing values for other individual data points will remain as missing unless otherwise specified. All analysis will be based on observed case unless otherwise stated.

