##### **9.1.4.2 cUTI**

- **Sustained Eradication:** A culture taken any time after documented eradication at TOC, and a urine culture obtained at FU shows that the baseline uropathogen found at entry at  $\geq 10^5$  CFUs/mL remains  $< 10^3$  CFUs/mL.
- **Recurrence:** A culture taken any time after documented eradication at TOC, up to and including FU that grows the baseline uropathogen  $\geq 10^3$  CFUs/mL.
- **Indeterminate:** No urine culture or subject received additional antibacterial therapy for the treatment of the current infection. Indeterminate at TOC will be carried forward.
- **Persistence:** Persistence at TOC will be carried forward.

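### Protocol 8.4 makes the follow-up culture conditional, but sustained eradication in cUTI requires one, so clinically well patients left uncultured would count as non-responders at follow-up

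*Protocol*

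**What the plan says.** **When the culture is taken.** Protocol 8.4, the FUP visit list, has "Biologic tissue or fluids (including blood until result is negative) for microbiological culture (if indicated"). Protocol 8.3, the TOC list, has the same item with no such condition: "Biologic tissue or fluids (including blood until result is negative) for microbiological culture". Protocol 7.7.1 says that after treatment starts "appropriate clinical specimens will be obtained at the specified assessment time points (EA, EOT, TOC, FUP"). Appendix 1 marks a culture at FUP, and its culture footnote limits only repeat blood cultures. Protocol 7.15 sends the reader to Appendix 1 for the timing of efficacy measurements.

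**How the cUTI outcome is scored.** Under Protocol 7.11.4.2, sustained eradication needs documented eradication at TOC "and a urine culture obtained at FUP shows that the baseline uropathogen found at entry at" or above the entry threshold has stayed below the eradication threshold. The Indeterminate category there covers "No urine culture or patient received additional antibacterial therapy for the treatment of the current infection including missed sampling". SAP 9.1.4.2 agrees: "No urine culture or subject received additional antibacterial therapy for the treatment of the current infection".

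**How Indeterminate is counted.** Under SAP 6.4.2, missing and indeterminate outcomes "will be included in the denominator as indeterminate for cure/eradication rate, i.e., considered as not responders". In SAP Table 9-3, indeterminate microbiology with sustained clinical cure gives a composite of Indeterminate, which is not a response either.

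**The other infection sites.** SAP 9.1.4.1 and 9.1.4.3 presume eradication in a clinically successful patient when no culture can be obtained (pneumonia, sepsis) or when the investigator sees no further need for one (BSI). cUTI has no such rule.

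**The concern.** The visit list makes the culture optional, while the endpoint definition makes it essential. Section 8.4 also asks for the microbiological outcome at FUP without condition, so the outcome is compulsory and its only input is not.

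A recovered cUTI patient is the one in whom a site is least likely to see a reason for a culture. Read literally, 8.4 lets that patient go uncultured, and the scoring rules then remove the patient from the response numerator. The FUP eradication and composite rates would fall for a reason unrelated to treatment. Because investigators know the treatment, their view of who needs a culture could also differ by arm.

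**Working it through.** **1. Inputs from the documents.** About 150 patients are randomized 2:1, which gives 150 × 2/3 = 100 on S-649266, the plan's own figure. cUTI is capped at 30% of randomized patients: 0.30 × 150 = 45, or about 30 v 15 by arm. The plan states no power, no effect size, and no expected FUP rate or culture rate.

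**2. The path of one patient.** Take a cUTI patient eradicated at TOC and well at FUP, with no urine culture at FUP.
- Per-pathogen outcome: Indeterminate (Protocol 7.11.4.2, SAP 9.1.4.2).
- Per-subject outcome: Indeterminate (SAP 9.1.6).
- Eradication rate: in the denominator, not in the numerator (SAP 6.4.2).
- Composite: Indeterminate (SAP Table 9-3), so not a response (SAP 9.4.1.5).
- Clinical outcome: still sustained clinical cure.

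**3. Whether another planned analysis removes this.** None does. The supplementary cUTI definitions keep the patient Indeterminate (SAP 9.2.5.2, no assessment; SAP 9.3.2.2, no urine culture). The CR-ME population requires a TOC assessment, not an FUP culture.

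**4. Size.** Let p be the true sustained eradication rate and m the share of truly eradicated patients with no FUP culture. Both are assumptions. The reported rate is R = p × (1 − m), and the loss is p × m.

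| m | R at p = 60% | R at p = 70% |
|---|---|---|
| 0% | 60% | 70% |
| 10% | 54% | 63% |
| 20% | 48% | 56% |
| 30% | 42% | 49% |
| 50% | 30% | 35% |

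Over the wider range p = 50% to 80% and m = 10% to 50%, the loss runs from 0.50 × 0.10 = 5 points to 0.80 × 0.50 = 40 points.

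**5. Per patient, at the cap.** One uncultured well patient costs 1/30 = 3.3 points on S-649266 or 1/15 = 6.7 points on BAT.

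**6. Unequal skipping.** With p = 60% in both arms and m = 10% v 30%, the reported rates are 54% v 42%, a gap of 0.60 × (0.30 − 0.10) = 12 points with no true difference. Reversing the arms reverses the sign. At p = 70% the gap is 63% − 49% = 14 points.

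**7. Precision, for scale.** With full culturing and p = 60%, the Clopper-Pearson 95% intervals are 40.6% to 77.3% for 18/30 and 32.3% to 83.7% for 9/15.

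**The case against.** Section 8.4 does not stand alone. Protocol 7.15 makes Appendix 1 the schedule for efficacy measurements, and Appendix 1 has no such condition at FUP. Since 8.4 also requires the microbiological outcome, and in cUTI that needs a urine culture, a site could reasonably treat the culture as always indicated. This stands: skipping is one possible reading, and the loss is conditional on it. It does not remove the conflict. The qualifier looks deliberate, because at TOC only the chest radiograph carries it, while at FUP both the radiograph and the culture do. Nor can it refer to blood alone, since blood has its own qualifier within the same item.

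The consequence is also limited. The FUP rates are secondary and descriptive, reported with 95% CIs by arm. The only comparison that the SAP specifies is the survival and no-change composite at TOC. The intervals are wide at this sample size. Counting missing as non-response is a stated, conservative convention. All of this stands and bounds the importance of the point.

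Some remedy already exists. Outcome categories are summarized by arm, so the Indeterminate count should be visible, and Protocol 7.7.1 requires the reason for an unobtained specimen in the eCRF. What is missing is a split of Indeterminate by cause.

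A reader might infer that well patients are turned into failures. The documents do not support that: they are Indeterminate, not Recurrence, Persistence or composite Failure. A reader might also infer that the FUP rates are biased as a matter of fact, or that a gap between arms is to be expected. Neither follows, because no skipping rate or direction is given.

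**Conclusion.** The inconsistency is real. Protocol 8.4 conflicts with 7.7.1 and Appendix 1, and in cUTI the conflict matters because the culture cannot be replaced and its absence is scored as non-response. Where sites follow 8.4, clinically well cUTI patients become non-responders, which lowers the secondary FUP microbiological rates (per patient and per pathogen) and the FUP composite. Unequal skipping by arm is possible in an open-label study but is not shown.

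The size rests on assumptions. At a true rate of 60% to 70%, skipping of 10% to 50% gives reported rates of 30% to 63%. The figures of 3.3 and 6.7 points per patient rest on the cUTI cap being filled and split 2:1. They are larger if fewer patients enter the analysis population.

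The primary cUTI endpoint is not affected. It is assessed at TOC, where 8.3 lists the culture without condition.

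**What to change.** 1. Reconcile Protocol 8.4 with 7.7.1 and Appendix 1 so that the FUP urine culture is unconditional for cUTI. Make the wording for other specimen types agree across the three places as well. Lifting the condition for urine alone would leave the conflict in place for the rest.
2. In the SAP, report by arm the number of cUTI patients who are Indeterminate at FUP because no culture was taken, separately from other causes.
3. Add a supplementary FUP eradication rate among cUTI patients cultured at FUP, with a note that this subset may be selected. If symptomatic patients are the likelier to be cultured, it leans toward recurrence, so it complements the main rate and does not replace it.

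The cost is small: a wording change with no new procedure, since 7.7.1 and Appendix 1 already schedule the culture, plus one table row and one supplementary rate. If data collection is already complete, items 2 and 3 can still be done.

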## **8.5 End of Study (EOS [EOT + 28 days])**

- Limited physical examination relevant to the patient's current condition
- Vital signs (including blood pressure, body temperature, pulse rate, and respiratory rate)
- Clinical laboratory tests (hematology, blood chemistry, and urinalysis; see Table 7-1) if required to follow abnormal safety test results
- AE assessment
- Concomitant therapy
- Hospitalization
- Vital status (survival or death)

EOS assessments may be performed by phone to document current patient status, in which case, the physical examination, vital signs, and laboratory tests will not be performed. Any AEs ongoing at EOS (28 days after the last dose of study treatment) will be followed as specified in Section 7.12.2. Continuing laboratory changes that are considered significant and symptoms related to AEs should be followed until resolution, AEs are judged by the investigator to have stabilized, or the patient is lost to follow-up. Pregnancies should be followed as specified in Section 7.12.9.

## 9. PLANNED STATISTICAL METHODS

### 9.1 General Considerations

The statistical efficacy analysis and PK analyses will be performed by the sponsor or designee. The detailed statistical analysis methods will be specified in a statistical analysis plan (SAP). Deviations from analyses outlined in the protocol will be detailed and justified in the SAP. The SAP will be finalized before scheduled database lock. A separate detailed PK/PD analyses plan will also be prepared.

Unless otherwise noted, continuous variables will be summarized by using the number of non-missing observations, arithmetic mean, standard deviation (SD), median, minimum, and maximum values as descriptive statistics; categorical variables will be summarized by using the frequency count and the percentage of patients in each category as descriptive statistics.

All patient study data, including data not appearing in tables, will be presented in by-patient data listings. In general, all tables and associated graphics will be presented by treatment group. Individual patient data, PK data, and any derived data will be presented by treatment and patient. All analyses and tabulations will be performed by using SAS Version 9.2 or higher, Phoenix WinNonlin Version 6.2.1 or higher and NONMEM Version 7.3 or higher.

If statistical tests are performed, they will be performed at the 0.05 significance level using 2-sided tests, except where otherwise noted. No multiplicity adjustment of statistical tests will be applied in this study.

